11.6.2 Additional Efficacy and Outcome Research Analyses

FI-2

Changes in muscle endurance measured by FI-2 scores over time in the study will be assessed using a longitudinal repeated measures mixed model. The model will include baseline FI-2 score, double-blind treatment group, randomization stratification factors disease diagnosis (DM vs. Non-DM), ILD (absent vs present), Region (Japan vs ROW), time and time by treatment interaction. The estimate of baseline mean FI-2 score, mean post-baseline FI-2 score, and adjusted mean change from baseline FI-2 score will be summarized by treatment group and visit. Treatment difference in adjusted mean changes from baseline, along with the corresponding 95% confidence intervals, will also be presented.

Myositis Response Criteria

To assess the myositis response criteria score over time during the study a longitudinal repeated mixed effects model will also be used. The mixed model will include double-blind treatment group and randomization stratification factors: disease diagnosis (DM vs. Non-DM), ILD (absent vs present), Region (Japan vs ROW), time (study days in which MRC is measured) and time by treatment interactions as fixed effects and subject as a random effect. Adjusted mean difference, SE, 95% CI for adjusted mean difference between treatment groups will be provided. The estimate of mean post-baseline MRC total improvement score will be also summarized by double-blind treatment group and visit.

[REDACTED]

[REDACTED]

[REDACTED]

[REDACTED]

[REDACTED]

[REDACTED]

post-baseline MDI, and adjusted mean change from baseline MDI score will be also be presented

[REDACTED]

[REDACTED]

[REDACTED]

[REDACTED]

[REDACTED]

[REDACTED]

[REDACTED]

11.7 Safety

Unless otherwise specified, the same safety analyses for the Week 24 analysis will be performed for AEs that occurred during the open-label / open-label extension / long-term extension periods.

Additional analyses will also be provided for the cumulative Abatacept period in subjects who received at least one dose of Abatacept at any time during the study. The analyses in addition to the safety analyses for Week 24 analysis described in [Section 7.6](#) are explicitly summarized in the following:

- Incidence rates by 3-month intervals for SAEs, pre-specified infections and adverse events of interest (*Infections, Malignancy, Autoimmune disorders*) will be provided for cumulative abatacept period.
- Multiple events will be reported based on unique AEs for each specific preferred term. For each subject and preferred term, a single record (unique AE) is used to represent multiple AEs when:
 - Multiple AE records have the same onset date.
 - The onset date of an event record is either the same day or 1 day later than the resolution date of a preceding event record (continuous events).
 - The onset date of an event record is after the onset date and prior to or on the resolution date of a preceding event record (overlapping events).

The unique AE record contains the earliest onset date, latest resolution date (if available), highest intensity, latest relationship, the most severe adverse event type (i.e., the SAE if ever reported as SAE), treatment required (will be yes if ever required) and highest action taken in the following order (highest to lowest): drug discontinued, drug interrupted, dose reduced, dose increase, none.

Multiple events will be presented for the cumulative abatacept period based on subjects who received at least one dose of abatacept at any time during the study.

Exposure adjusted (per 100 person-years) incidence rates of adverse events accounting for multiple occurrence of an event will be calculated for all AEs/SAEs which occurred during the open-label / open-label extension / long-term extension periods in abatacept treated subjects. The numerator is the number of unique events within the open-label / open-label extension / long-term extension periods (up to 56 days post last abatacept dose during the open-label / open-label extension / long-term extension periods). The denominator is the overall total exposure (person-years) within each period, which is calculated as the sum over all subjects of exposure (in days) divided by 365.25. The resulting incidence rate is multiplied by 100 to express the rate per 100 person-years.

As an example, if 10 patients report 7 unique episodes of headache and had a combined cumulative exposure of 20 years to study medication, the incidence rate is reported as $7 / 20 * (100)$ or 35 cases per 100 patient years of exposure.

For all SAEs, exposure adjusted per 100 person-years rates will be summarized by time-intervals in months: 0-3 months, 3-6 months, 7-9 months, 10-12 months and > 12 months (time-intervals defined as Days 1-90, Days 91-180, Days 181-270, 271-360 and > 360 Days), respectively. In addition, the number of subjects who experienced a SAE, once or multiple times within this period will be presented. The above analyses will be performed for infection and local injection site reaction, respectively. A subject listing of unique AEs will also be provided.

Unique AEs and exposure adjusted multiple events summaries will also be provided separately for the cumulative period. The exposure adjusted per 100 person-years rates will be provided for SAEs, Infections, local injection site reaction. and will be summarized by 3 month time interval for the cumulative period: 0-3 months, 3-6 months, 7-9 months, 10-12 months and > 12 months (time-intervals defined as Days 1-90, Days 91-180, Days 181-270, 271-360 and > 360 Days), respectively.

[REDACTED]

[REDACTED]

- █ [REDACTED]
- █ [REDACTED]
- █ [REDACTED]
- █ [REDACTED]
- █ [REDACTED]

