#### 3.1 Study Design and Duration

This is a 24 week, Phase 3, randomized, double-blind, placebo-controlled, multicenter, study in subjects with active Idiopathic Inflammatory Myopathy (IIM; eg, DM, PM, autoimmune necrotizing myopathy; see Section 3.3.1) on standard background treatment.

In addition to the 24-week double-blind period, the study includes a 28 week open-label treatment period during which all subjects will receive SC abatacept with background treatment, an additional 24 weeks open label of SC abatacept with continued therapy from the original OL period for subjects in Japan, and a 3 year long term extension of SC abatacept (156 weeks) with background treatment for all subjects except subjects in the U.S. and the Czech Republic.

The primary objective for this study is to compare the clinical efficacy of weekly abatacept in combination with standard treatment to standard treatment alone by assessing the percentage of subjects who achieve the IMACS DOI after 24 weeks of treatment versus standard treatment alone in adult subjects with active IIM. The study design schematic is presented in Figure 3.1-1.

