### **3.1.3 Open-Label Period (Week 24 - Week 52) and Open-Label Extension Period (Week 52 - Week 76) for Japan**

The 24-week Double-Blind Period is followed by a 28 week open-label abatacept treatment period (Open-Label Period, see [Table 5.1-3](#)). During this period, subjects initially randomized to receive

the combination of abatacept and standard treatment will continue this regimen. Subjects who are initially assigned to receive standard treatment alone will be switched to standard treatment plus abatacept.

There will also be a 24 weeks (168 days) open label extension for subjects randomized in Japan.

Background treatment may be adjusted (including the dose of corticosteroids and immunosuppressants) at any time during this period. Use of immune globulin (intravenous [IVIG] or subcutaneous [SCIG] is permitted during this period. Addition of any other prohibited medication ([Section 3.4.2.1](#)) is not permitted.

During this period, subjects who have clinically active or relevant interstitial lung disease (ILD) or anti-synthetase syndrome as determined by the investigator, may have to repeat pulmonary function testing and HRCT scan of the chest at Wk 52. (See [Section 5.3.6](#) and [Section 5.3.7.2](#)) and at Wk 76 for Japan.

Subjects who participate in the sub-study of MRI muscle (thigh) imaging will have an MRI performed at Wk 52. See [Section 5.8.2](#)

Subjects who discontinue treatment with abatacept during the Open-Label Period or Open Label Extension for Japan will complete the Early Termination visit for the OL (See [Table 5.1-3](#) day 365 is also the OL ET) and 2 follow-up visits during the 24 week post-treatment follow-up period, to perform safety and laboratory assessments. (See [Table 5.1-7](#)). If the subject receives treatment with an alternate source of abatacept (Post-Study Drug Program [PSDP] or Commercial), completing this post-treatment follow-up period is not required.

Treatment with other biologic therapy is not recommended for at least 70 days (~5 half-lives of abatacept follow-up period.

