#### **8.4.9 Long Term Open Label Extension (3 Years)**

The analysis will be performed when all subjects have completed a total of 3 years open label treatment in the Long Term Open-Label Extension and/or the follow-up period of the study. The analysis will include safety. No formal statistical testing will be conducted; appropriate summary statistics will be provided. Safety summaries will include events reported from the start of the Long Term Open-Label Period up to 56 days post last dose date.

Cumulative abatacept safety summaries will also be provided for all subjects who received abatacept at any time during the study. The cumulative safety summaries will include all AEs reported from the first dose of abatacept up to 56 days post the last dose of abatacept in the study.

The analyses will be based on open-label treated analysis population except for the cumulative abatacept safety summaries which will be based on all subjects who received at least one dose of abatacept at any time during the study.

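### SAP 11.7 pools all abatacept time after Day 360 into one interval, so its rate tables cannot show a trend within the second and later years of exposure

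*SAP*

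**What the plan says.** SAP 11.7 speaks to rates over time in two places.

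- An early bullet, for the cumulative abatacept period, plans "Incidence rates by 3-month intervals for SAEs, pre-specified infections and adverse events of interest", naming infections, malignancy and autoimmune disorders as the events of interest. It gives no last interval.
- Later paragraphs set out exposure-adjusted rates per 100 person-years and define the intervals: "10-12 months and > 12 months (time-intervals defined as Days 1-90, Days 91-180, Days 181-270, 271-360 and > 360 Days". This definition appears twice, once with the open-label, open-label extension and long-term extension periods and once for the cumulative period. For the cumulative period, "The exposure adjusted per 100 person-years rates will be provided for SAEs, Infections, local injection site reaction". Malignancy and autoimmune disorders are not in that list.

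The section also plans an overall rate for each study period ("The denominator is the overall total exposure (person-years) within each period") and an event-level output: "A subject listing of unique AEs will also be provided".

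On duration, Protocol 3.1 states that "In addition to the 24-week double-blind period, the study includes a 28 week open-label treatment period", followed by a 156-week long-term extension outside the US and the Czech Republic. Protocol 3.1.3 adds for Japan: "There will also be a 24 weeks (168 days) open label extension for subjects randomized in Japan". For the long-term extension, Protocol 8.4.9 says "The analysis will include safety" and mentions no efficacy analysis; SAP 11.6 likewise covers efficacy only for the open-label and open-label extension periods.

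**The concern.** Safety over time is what the long-term extension contributes. The interval scheme gives four columns to roughly the first year on abatacept and one column to everything after it, which for a subject who completes the extension is about three years. If the rate of serious events or infections climbed, or fell, during those years, the table by time on drug would return a single average. For illustration, with assumed rates and equal person-years, yearly rates of 4, 8 and 12 per 100 person-years give (4 + 8 + 12)/3 = 8, the same as a flat rate of 8.

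The early bullet in 11.7 does not settle the matter. It could be the same table, with the later paragraph defining its intervals, or a separate table that runs to the end of follow-up. A programmer cannot tell which, and the event lists differ.

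**Working it through.** **The plan's own figures.** The Synopsis gives 4.5 years of treatment. The longest path (Japan) is 24 + 28 + 24 + 156 = 232 weeks; 232 × 7 / 365.25 = 4.45 years, which agrees. Without the Japan extension, 208 × 7 / 365.25 = 3.99 years. The worked rate in SAP 11.7 also reproduces: 7/20 × 100 = 35 per 100 patient-years.

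**Inputs.**
- The last long-term extension dose is on Day 1086 of that period, and the last open-label dose is in Week 51 (Protocol 4.5.1).
- The cumulative period runs from the first abatacept dose to the last dose + 56 days. For the placebo arm it starts at the first open-label dose (SAP 6.1).
- Abatacept days before the long-term extension: outside Japan, 52 × 7 = 364 (abatacept arm) and 28 × 7 = 196 (placebo arm); in Japan, 76 × 7 = 532 and 52 × 7 = 364.

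**Formula.** Total days = days before the extension + 1086 + 56. Share in the open interval = (total − 360) / total.

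| Completer | Total days | Days after 360 | Share |
|---|---|---|---|
| Outside Japan, abatacept arm | 1506 | 1146 | 76.1% |
| Outside Japan, placebo arm | 1338 | 978 | 73.1% |
| Japan, abatacept arm | 1674 | 1314 | 78.5% |
| Japan, placebo arm | 1506 | 1146 | 76.1% |
| US/Czech, abatacept arm | 51 × 7 + 1 + 56 = 414 | 54 | 13.0% |
| US/Czech, placebo arm | 27 × 7 + 1 + 56 = 246 | 0 | 0% |

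Without the 56-day tail, the first four shares are 1090/1450 = 75.2%, 922/1282 = 71.9%, 1258/1618 = 77.8% and 75.2%; both US/Czech shares are 0%.

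**Period tables.** SAP 11.7 does not say where Day 1 falls.
- If the clock restarts at the first long-term extension dose, 782/1142 = 68.5% of that period is in the open interval and its first year is split by quarter. The open-label table would then have nothing in its last two columns, because 28 × 7 + 56 = 252 days is below 271.
- If the clock runs from the first abatacept dose, the long-term extension lies wholly after Day 360 for the abatacept arm (it starts on Day 365 outside Japan). For the placebo arm outside Japan, 360 − 196 = 164 of its 1142 days come earlier, leaving 978/1142 = 85.6% in the open interval.

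**Effect of finer intervals.** With yearly (360-day) blocks, the largest block is 360/1674 = 21.5% to 360/1338 = 26.9% of a completer's exposure.

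Precision depends on retention and event rate, which the documents do not give. Assume 100 to 150 subjects on drug and 5 to 10 events per 100 person-years:
- A 90-day interval holds 100 × 90/365.25 = 24.6 to 150 × 90/365.25 = 37.0 person-years, or about 1.2 to 3.7 events.
- A 360-day block holds four times as much: 98.6 to 147.8 person-years, or about 4.9 to 14.8 events.

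Yearly blocks are therefore a better choice than quarters after the first year.

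**The case against.** The case for leaving the plan alone has real content. A reader might infer that late signals cannot be seen at all, or that a rise in years 2 to 4 would be diluted by first-year time. The documents support neither reading.

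- The open interval contains only time after Day 360, so a higher rate there than in the four earlier columns would be visible.
- The long-term extension has its own overall rate, which can be set against the open-label rate.
- The adverse event listings in SAP 7.6, carried forward by 11.7, give onset day relative to the start of dosing, and an independent data monitoring committee reviews safety (SAP Section 1).

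A reader might also take the three-quarters share as applying to everyone. It does not apply to US and Czech completers, or to subjects who stop early. Nor can it be said flatly that the intervals end at month 12, because the early bullet sets no end. Text at the end of 11.7 is blacked out, so further summaries cannot be excluded. Pooling sparse late time is also a defensible instinct, and no formal testing hangs on these tables.

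What this leaves standing is narrower. A listing has no person-years, and one rate per study period has no time axis. None of the visible outputs certainly gives a rate by time within years 2 to 4. Only the early bullet might, and the more natural reading is that the later paragraph defines its intervals.

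**Conclusion.** The point holds in a limited form. The tables defined in SAP 11.7 cannot show a trend within the second and later years of abatacept exposure. For completers who enter the long-term extension, those years are 73.1% to 78.5% of exposure with the 56-day tail (71.9% to 77.8% without it). They would still show a step up after the first year or between the open-label and long-term extension periods.

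The shares assume dosing on schedule to Day 1086, no gap long enough to trigger the exposure adjustment in SAP 11.5.1.4, and the cumulative clock defined in SAP 6.1. The conclusion also assumes that the blacked-out text adds no finer table. Separately, the two statements in 11.7 disagree on end point and event list whichever way the first is read. This is a cheap improvement to descriptive safety output, with no bearing on the primary analysis.

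**What to change.** In SAP 11.7:

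1. For the cumulative and long-term extension tables, replace the open category with yearly intervals to the end of follow-up, for example 13-24, 25-36, 37-48 and over 48 months, and show person-years in each.
2. Reconcile the early bullet with the later paragraph by using one interval scheme for all the events named in either, including malignancy and autoimmune disorders.
3. State the time origin for the period-specific tables: first dose in that period or first abatacept dose.

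The cost is a few extra columns and some programming, with no new data. Late intervals will be sparse. The last would hold 1506 − 1440 = 66 days for an abatacept-arm completer outside Japan, 1674 − 1440 = 234 days for one in Japan, and nothing for a placebo-arm completer outside Japan (1338 days). Showing the person-years lets the reader judge how much weight each rate can bear.
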